
7. Activity. Please mark the stage.
 
  
 	stage 0	stage 1	stage 2	stage 3	stage 4	
   
 Prurigo lesions with excoriations/crusts compared to all prurigo lesions	0 %	1- 25 %	26 - 50 %	51 - 75 %	76 - 100 %	
 
 Healed prurigo lesions compared to all prurigo lesions	100 %	75-99 %	50 - 74 %	25 - 49 %	0 - 24 %	
  
			stage 0	stage 1	stage 2	stage 3	stage 4	Prurigo lesions with excoriations/crusts compared to all prurigo lesions	0 %	1- 25 %	26 - 50 %	51 - 75 %	76 - 100 %	Healed prurigo lesions compared to all prurigo lesions	100 %	75-99 %	50 - 74 %	25 - 49 %	0 - 24 %
	stage 0	stage 1	stage 2	stage 3	stage 4														
Prurigo lesions with excoriations/crusts compared to all prurigo lesions	0 %	1- 25 %	26 - 50 %	51 - 75 %	76 - 100 %														
Healed prurigo lesions compared to all prurigo lesions	100 %	75-99 %	50 - 74 %	25 - 49 %	0 - 24 %														

8. Take photos of the patient: Overview front and back, area(s) of marked monitor lesions to recognize on next visit
																			

Patient Benefit Index, Pruritus Version (PBI-P)

Sample – actual assessment scale will be provided to the patient at appropriate visits

Importance of Treatment Goals

With the help of the following questions, we'd like to know how important the goals mentioned below are to you personally in the **current treatment** of your skin disease.

For each of the following statements, please mark **how important** this treatment goal is to you.

If a statement does not apply to you, for example because you are not experiencing pain, please mark "does not apply to me".

As a result of therapy, how important is it for you to...		not at all	somewhat	moderately	quite	very	does not apply to me
1	...be free of pain						
2	...be free of itching						

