17	...be able to lead a normal working life						
18	...be able to have more contact with other people						
19	...be more comfortable showing yourself in public						
20	...be less burdened in your partnership						
21	...be able to have a normal sex life						
22	...be less dependent on doctor and clinic visits						
23	...need less time for daily treatment						
24	...have fewer out-of-pocket treatment expenses						
25	...have fewer side effects						
26	...find a clear diagnosis and therapy						
27	...have confidence in the therapy						

Please recheck your answers to make sure you have clearly marked each statement with an "x".

Thank you very much for your cooperation!

PBI-P (Cont'd)

Sample – actual assessment scale will be provided to the patient at appropriate visits

Treatment Benefits

When the treatment began, you indicated in a questionnaire how important various goals were in the treatment of your skin disease.

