Please mark each of the following statements according to the extent to which those treatment goals **were achieved**, indicating if the treatment has benefited you. If a statement did not apply to you, for example because you did not experience any pain, please mark "did not apply to me".

The current treatment has helped me to ...		not at all	somewhat	moderately	quite	very	did not apply to me
1	...be free of pain						
2	...be free of itching						
3	...no longer have burning sensations on my skin						
4	...be healed of all skin defects						
5	...concentrate better						
6	...be less nervous						
7	...be able to wear all types of clothing						
8	...be able to bathe and shower normally						
9	...sleep better						
10	...feel less depressed						
11	...experience greater enjoyment of life						
12	...have no fear that the disease will get worse						

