	
Treatment Period after participating in the Observation Period for any length of time.
 
 • Assess skin lesion improvement using the metrics of the PAS • Change from Baseline in Patient-Reported Outcome measures Worst itch NRS, average itch intensity NRS, VRS (itchy, burning and stinging), MOS Sleep-R, ItchyQoL, HADS) by Treatment Period study visit and Baseline NRS score • Change between Baseline and final Treatment Period visit in PBI-P • A description of the percentage of patients utilizing various doses of nalbuphine HCl ER tablets by Study Week • A description of the frequency and reasons for dose up- and down-titration and treatment discontinuation during the study • Frequency and distribution by time on study of patients determined to meet failure to improve criteria • Changes in the PRO measurements during the Washout Period after cessation of treatment of nalbuphine HCl ER tablets • Time to the first use of rescue medications and the number of days of use of rescue medications for itching • To evaluate the daily changes in the Subjective Opiate Withdrawal Scale (SOWS) during the Washout Period after cessation of treatment of nalbuphine HCl ER tablets 
Exploratory Endpoint
 
 • Impact on the measurement of nerve fiber density (histology) and MOR/KOR density (histology, Western Blot), as well as histological (H&E) changes in skin biopsies taken at Baseline and the final Treatment Period Visit to investigate possible correlation with any clinical response and also compared to biopsy material assessed during study TR03 (optional procedures at select sites only).

Statistical Methodology
	
Efficacy:
 
All efficacy endpoints will be evaluated through the generation of summary statistics. For continuous variables, the mean, standard deviation, median, minimum, and

maximum will be presented for a particular visit and for the change from baseline (Visit 1a or 1b). For categorical variables, the number and percentage of patients within each category of classification will be summarized by study visit. No formal statistical testing will be conducted.

Safety:

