5.2 SECONDARY ENDPOINTS

Visit 1a or 1b will serve as the baseline visit for efficacy endpoints. Visit 1a will be the baseline for patients directly entering the Treatment Period as of Visit 1a. Visit 1b will be the baseline for patients entering the Treatment Period after participating in the Observation Period for any length of time.

- Assess skin lesion improvement using the metrics of the PAS
- Change from Baseline in Patient-Reported Outcome measures Worst itch NRS, average itch intensity NRS, VRS (itchy, burning and stinging), MOS Sleep-R, ItchyQoL, HADS) by Treatment Period study visit and Baseline NRS score
- Change between Baseline and the final Treatment Period visit in PBI-P
- A description of the percentage of patients utilizing various doses of nalbuphine HCl ER tablets by Study Week
- A description of the frequency and reasons for dose up- and down-titration and treatment discontinuation during the study
- Frequency and distribution by time on study of patients determined to meet failure-to-improve criteria
- Changes in the PRO measurements during the Washout Period after cessation of treatment of nalbuphine HCl ER tablets
- Time to first use of rescue medications and the number of days of use of rescue medications for itching
- To evaluate the daily changes in the Subjective Opiate Withdrawal Scale (SOWS) during the Washout Period after cessation of treatment of nalbuphine HCl ER tablets.

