9.6.2.2.12 TV 14 (End of Treatment Visit)

This visit applies to all patients who completed TV13; including patients who met Failure-to-Improve criteria at any Treatment Visit during the study.

For patients who DID NOT meet Failure-to-Improve criteria during the conduct of the study, this visit (TV14) takes place after the patient has completed study medication.

- For patients who entered the Treatment Period at Visit 1a, TV14 would take place during week 51; four (4) weeks after TV13, as these patients should complete 50 weeks of treatment prior to TV14
- For patients who entered the Treatment Period at Visit 1b see [Table 8](#) for information on when TV14 is to take place

The following procedures are to take place at this visit:

- obtain vital signs
- perform physical examination
- perform brief neurological assessment
- complete the PAS
- perform 12-lead ECG after at least 5 minutes in a supine position (See the Study Reference Manual for ECG procedures, [section 17.4](#) Electrocardiograms for the handling of Cardiovascular adverse events)
- collect blood for central laboratory (hematology and chemistry) and serum pregnancy test for central laboratory
- collect urine for urinalysis at the central laboratory
- collect blood for PK
- at select sites only, perform skin biopsy (optional). Obtain 3 samples (i.e., H&E, nerve fiber density (histology) and MOR/KOR density (histology, Western Blot)); see the Lab and Study Reference Manuals for details
- administer PRO measurements:
 - Worst itch NRS
 - Average itch intensity NRS
 - VRS
 - ItchyQoL
 - MOS Sleep-R
 - HADS
 - SOWS

The PRO questionnaires must be administered at the study site under the supervision of and by trained study staff, strictly adhering to PRO Administration Instructions (see Study Reference Manual).

- record AEs

- review of concomitant medications, including over-the-counter medications, nutritional supplements, and vitamins
- perform study drug accountability, final retrieval of any dispensed study drug
- retrieve the Dosing Diary
- Dispense the 14 Day SOWS packet, instruct the patient on how to complete the scales and to complete the scales daily for 14 days
- Schedule the patient for the Washout and Safety Follow-up Period Visit

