9.7.7.6 Patient Benefit Index (PBI-P)

The PBI-P questionnaire assesses the importance of treatment objectives to the individual. Before and at the end of drug treatment in this study, the patient completes the same questionnaire and rates the extent to which the treatment objectives have been achieved. The instrument consists of 27 multiple choice questions that can be answered “not at all”, “somewhat”, “moderately”, “quite” and “very”. The instrument can be found in [Appendix 4](#).

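### The PBI-P endpoint is defined as a change from baseline, but the instrument rates importance before treatment and benefit after it; the TV14 procedure list also omits it

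*Protocol*

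**What the plan says.** Sections 4.2 and 5.2 of protocol Version 2.0, and the synopsis, list as a secondary item "Change between Baseline and the final Treatment Period visit in PBI-P". Baseline is Visit 1a or Visit 1b. For continuous efficacy variables, the synopsis gives the reporting rule: the mean, standard deviation, median, minimum and "maximum will be presented for a particular visit and for the change from baseline (Visit 1a or 1b".

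Section 9.7.7.6 describes the instrument in two sentences that do not agree. The first: "The PBI-P questionnaire assesses the importance of treatment objectives to the individual". The second says that, before and at the end of drug treatment, "the patient completes the same questionnaire and rates the extent to which the treatment objectives have been achieved".

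Appendix 4, which is available only in the Version 1.0 text, reproduces two forms. The Importance of Treatment Goals form says the study would "like to know how important the goals mentioned below are to you personally in the" current treatment. The Treatment Benefits form opens with "When the treatment began, you indicated in a questionnaire how important various goals were in the treatment of your skin disease" and continues "Please mark each of the following statements according to the extent to which those treatment goals" were achieved.

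In Version 2.0 the PBI-P is on the procedure lists for Visit 1a (9.6.1), Visit 1b (9.6.4) and the Early Termination Visit after withdrawal of consent (9.6.7). Under "administer PRO measurements" at TV14 (9.6.2.2.12), the list has worst and average itch NRS, VRS, ItchyQoL, MOS Sleep-R, HADS and SOWS, but no PBI-P.

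**The concern.** A change from baseline needs the same quantity measured at both times. Here the first form measures what the patient wants from treatment and the second what treatment delivered. If the endpoint is computed as worded, high importance ratings at the start count against the result at the end, and the sign and size of the figure cannot be read as improvement or deterioration.

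The description of a single questionnaire adds a practical risk. A site that follows 9.7.7.6 literally could give the importance form again at the end, and benefit would not be recorded.

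The TV14 list raises the same risk. TV14 is the end-of-treatment visit both for patients who complete treatment and for those stopped under the failure-to-improve rule, so the benefit form has to be given there if the endpoint is to exist.

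**Working it through.** The protocol gives no figure for this endpoint, so the check is a comparison of texts plus a small illustration.

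**Step 1. What is measured, and when.**

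| | Before treatment | End of treatment |
|---|---|---|
| Importance of each of 27 goals | rated | not rated again |
| Benefit achieved on each of 27 goals | not rated | rated |

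The Treatment Benefits form itself places the importance rating at the start of treatment. No row has two entries, so no within-patient change can be formed on either quantity.

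**Step 2. What subtraction would give.** Each form has five ordered responses plus a not-applicable option. The protocol assigns no numbers. Assume 0 for the lowest response, 4 for the highest, and let d = benefit − importance for one goal.

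| Importance | Benefit | d |
|---|---|---|
| 4 | 4 | 4 − 4 = 0 |
| 0 | 0 | 0 − 0 = 0 |
| 4 | 0 | 0 − 4 = −4 |
| 0 | 4 | 4 − 0 = +4 |

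- Full success on a goal that matters scores the same as no benefit on a goal that does not.
- At fixed importance, d rises with benefit. At fixed benefit, d falls as importance rises.
- A patient who rates every goal at 4 cannot score above 4 − 4 = 0.
- On items answered at both times, the group mean of d equals mean benefit minus mean importance. A negative mean says only that the second average is below the first.
- A not-applicable response on either form cannot be subtracted.

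The pattern does not depend on the exact codes. It holds for any increasing code applied in the same way to both forms.

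**Step 3. Contrast with a weighted benefit.** Take two patients with two goals each, both with importance ratings (4, 0). Patient A has benefit (4, 0) and patient B has benefit (0, 4).

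- Mean d: A = (0 + 0)/2 = 0; B = (−4 + 4)/2 = 0.
- Importance-weighted benefit, Σ(importance × benefit)/Σ(importance): A = (4×4 + 0×0)/(4 + 0) = 4; B = (4×0 + 0×4)/(4 + 0) = 0.

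The difference cannot tell apart a patient who gained the one thing wanted from a patient who did not. The weighted score can.

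**Step 4. Collection at TV14.**

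| Source | PBI-P at the last treatment visit |
|---|---|
| Version 1.0, 9.6.2.2.4 text list | absent |
| Version 1.0, Table 6 | marked |
| Version 2.0, 9.6.2.2.12 text list | absent |
| Version 2.0, Table 6 | not in the text at hand |

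The Version 2.0 lists differ from those of Version 1.0 by adding SOWS at TV14 and the PBI-P at early termination. The gap at TV14 remains.

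**The case against.** **Scoring belongs in the SAP.** Section 19.1 (Version 1.0 text) leaves detailed methods to an SAP that is not at hand, and no subtraction formula is written down. The PBI-P also has its own bullet, apart from the other patient-reported outcomes, and 9.7.7.6 does mention achievement of goals. An SAP could therefore score the instrument sensibly. This stands as far as scoring detail goes. It does not remove the point, because the protocol itself names the endpoint as a change and describes two forms as one.

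**The ranking.** A reader might infer that subtraction inverts the ranking of patients. It does not: at any fixed importance, more benefit still gives a higher score. The fault lies in comparisons between patients with different importance ratings. The 0 to 4 coding is also an assumption, not a protocol rule.

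**Missing forms.** A reader might also infer that nobody except patients who withdraw consent would complete the final form. The documents do not support that. Section 9.7.7.6 calls for completion at the end of treatment, and 9.7.7 ties administration to the Schedule of Events. Version 1.0 had the same gap in its text while its Table 6 marked the form at TV14, and the Version 2.0 table may do the same.

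**The replacement formula.** The documents give no scoring rule, so the weighted score proposed here is one reasonable choice and the instrument's own rule may be used instead.

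**Version.** The two forms are seen only in the Version 1.0 appendix. The Version 2.0 contents list still carries the PBI-P, with the next instrument two pages later (115 to 117), and the wording of the instrument section is the same in both versions. Carry-over is therefore likely but not verified.

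**Conclusion.** The concern holds. As worded, the PBI-P endpoint is not a change in any measured quantity, and the statement that one questionnaire is completed twice conflicts with the two forms in Appendix 4. Computed literally, the result would be uninterpretable, since equal scores can come from opposite experiences and importance counts against the patient.

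This rests on the Version 1.0 forms still being in use. The numerical illustration also assumes common increasing codes on both forms.

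The TV14 omission is a mismatch between the visit list and the rest of the protocol. It puts collection at risk and should be reconciled, but it is not evidence that the form goes uncollected.

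The consequence is modest. This is one descriptive secondary endpoint in an open-label study whose primary endpoint is treatment-emergent adverse events and which plans no formal testing.

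**What to change.** 1. In the synopsis and sections 4.2 and 5.2, replace the change endpoint with an end-of-treatment benefit score that uses the Visit 1a or 1b importance ratings only as weights. One form is Σ(importance × benefit)/Σ(importance) over applicable items; the instrument's own scoring rule is an alternative. State the item coding, how not-applicable responses on either form are handled, and what is done when all importance ratings are zero and the denominator vanishes.
2. Exempt the PBI-P from the general change-from-baseline summary. Report importance at baseline and the weighted benefit at the end of treatment.
3. Rewrite 9.7.7.6 to describe two forms: importance before treatment, benefit at the end.
4. Add the PBI-P Treatment Benefits form to the TV14 list in 9.6.2.2.12, name that form in 9.6.7, and check both against the Version 2.0 Table 6.

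The cost is a few lines of endpoint wording and one added item on a visit list. The form already exists.

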All patients on drug treatment will enter a 2-week wash-out and safety follow up period following end of the Treatment Period with procedures conducted according to the Schedule of Events (See [Appendix 1](#)).

Patients with a Worst Itch NRS score less than 5 (< 5) enter the Observation Period:

Patients with a Worst Itch NRS score < 5 at Visit 1a will enter into an extended screening period, Observation Period (no drug treatment), of the study and will be followed for up to 12 weeks (extended screening weeks). Visit 1a for these patients is also Observational Visit 1 (OV1). Subsequent visits will be defined as OV2, OV3 and OV4 and will occur at approximately monthly intervals for the next 3 months.

During this Observation period, patients who report an increase in their Worst Itch NRS with a score of ≥ 5 at any one of their Observation Visits and meet all other eligibility criteria will be able to enroll immediately into the Treatment Period of the study and Visit 1b procedures are to be performed. Patients will receive open-label Study Drug starting with an evening 30 mg dose (to be taken at home), after the Visit 1b procedures have been completed. Receipt of the first drug will indicate the start of their Treatment Period and enrollment into the study. The duration of the Treatment Period for such a patient will vary depending upon the visit at which they transition from the Observation Period to the Treatment Period.

Patients in the Observation Period whose Worst Itch NRS score remains <5 over the 12 extended screening weeks will be screen failed from the study at the end of that time period.

Failure to Improve Criteria:

Beginning on TV 3 and at every subsequent Treatment Visit, patients with a Worst itch NRS equal to or greater than (\geq) the Worst Itch NRS at Visit 1a (or at Visit 1b in the case of patient who require the Observation Visit period) will be discontinued from taking study drug. Subjects discontinued from taking study drug are to undergo the End of Treatment Visit (TV14), the Washout/Safety Follow-up Period assessment in two weeks and receive a follow-up Telephone Contact 30 days following end of study drug for final safety

	assessment.

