The incidence of AEs will be summarized through the presentation of proportions by MedDRA body system classification and preferred term. Vital signs and laboratory data will be summarized using continuous-based descriptive statistics (n, mean, SD, median, minimum, maximum). The extent and duration of use of rescue medications will be similarly summarized using descriptive statistics. Summary statistics for AEs with onset during the Observation Period will be separately summarized. No formal statistical analysis will be performed on safety outcomes; inferences, if any, will be derived through clinical review and interpretation.

TABLE OF CONTENTS

1	STUDY SYNOPSIS	5
	TABLE OF CONTENTS	13
	LIST OF TABLES	16
	LIST OF FIGURES	16
2	LIST OF ABBREVIATIONS	17
3	INTRODUCTION	19
3.1	PRURIGO NODULARIS AND STUDY RATIONALE	19
3.1.1	General Information on Prurigo Nodularis	19
3.1.2	Potential Mechanism of Prurigo Nodularis Pathophysiology	21
3.1.3	Rationale for Investigating Nalbuphine HCl ER in Prurigo Nodularis	24
3.2	NALBUPHINE	27
3.3	NALBUPHINE HCL ER TABLET CLINICAL DEVELOPMENT	28
3.3.1	Overall Summary	28
3.3.2	Clinical Study TR01 in Hemodialysis Patients and Healthy Volunteers	29
3.3.3	Additional Nalbuphine HCl ER Tablet Clinical Data	31
4	STUDY OBJECTIVES	32
4.1	PRIMARY OBJECTIVE	32
4.2	SECONDARY OBJECTIVES	32
4.3	EXPLORATORY OBJECTIVES	32
5	STUDY ENDPOINTS	33
5.1	PRIMARY ENDPOINT	33
5.2	SECONDARY ENDPOINTS	33
5.3	EXPLORATORY ENDPOINTS	33
6	NUMBER OF SITES AND PATIENTS	34
7	ESTIMATED STUDY DURATION	34
8	SELECTION CRITERIA	34
8.1	STUDY POPULATION	34
8.2	INCLUSION CRITERIA	34
8.3	EXCLUSION CRITERIA	35
9	STUDY PLAN	35
9.1	GENERAL STUDY DESIGN	35
9.2	RATIONALE FOR STUDY DESIGN	35
9.3	SAFETY MONITORING PLAN	37
9.4	RISK-BENEFITS	39
9.5	STUDY OVERVIEW	40
9.6	STUDY PROCEDURES	42
9.6.1	Visit 1a (Day 1 of Study Week 1)	43
9.6.2	Treatment Period (Treatment Weeks 1-50)	45
9.6.3	Observation Period (Extended Screening Weeks 1-12)	58
9.6.4	Transition to Treatment Period (Visit 1b)	59
9.6.5	Washout and Safety Follow-Up Period	61

9.6.6	Premature Discontinuation of Study Drug Follow-up Telephone Contact Visit	62
9.6.7	Early Termination Visit for Patients who Withdraw Consent.....	62
9.6.8	Unscheduled Visits	63
9.6.9	Schedule of Events.....	63
9.7	STUDY DRUG TREATMENT AND DRUG ACCOUNTABILITY.....	63
9.7.1	Study Drug Dosing	63
9.7.2	Down-Titration	66
9.7.3	Multiple Missed Doses	66
9.7.4	Overdose	66
9.7.5	Treatment Compliance.....	66

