9.6.2 Treatment Period (Treatment Weeks 1-50)

Patients who enter the Treatment Period on Visit 1a will be in the Treatment Period for up to 50 weeks and thus are eligible to receive study drug for up to 50 weeks.

Patients who enter the Treatment Period from the Observation Period will be in the Treatment Period for up to 46 Treatment Weeks. Patients enter the Treatment Period from an Observation Visit (OV) when their Worst itch NRS is greater than or equal to 5 (≥ 5).

Regardless of how many treatment weeks the patient was on study drug, all patients who enter the Treatment Period will complete End of Treatment Visit TV14. Since all patients must titrate to their maintenance dose over the first four weeks of the Treatment Period, Visits 1a/Visits 1b (TV 1) and TV 2 over the first four weeks of the Treatment Period will be common to all subjects in TR03ext regardless of when they enter into the Treatment Period. Patients who transition from the Observation Period to the Treatment Period at a respective Observation Visit will follow the Treatment Visit schedule outlined in [Table 8](#).

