9.7.6 Rescue Medications, Concomitant Medications, Prohibited Medications, and Pre-Medications

9.7.6.1 Rescue Medications

A secondary objective of the study is to quantitate the number of days of rescue medication use for itching during the course of nalbuphine HCl ER treatment. Rescue medications will be defined as those drugs, when used for the purpose of treating itch, that were required to be washed out prior to entry into TR03 (See [Table 9](#)). For the purposes of this study, any UV light treatment received will also be defined as a rescue medication.

If a medication is prescribed for chronic anti-pruritic use of greater than 2 weeks, the subject should be discontinued (see [Section 11.2](#)).

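### Rescue medication use is a raw count of days, although time on drug runs from about 4 to 50 weeks and depends partly on outcome and on rescue use itself

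*Protocol*

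**What the plan says.** Protocol version 2.0, section 5.2, names the endpoint as "Time to first use of rescue medications and the number of days of use of rescue medications for itching". Section 9.7.6.1 sets the counting window as the patient's own course of drug: it refers to "the number of days of rescue medication use for itching during the course of nalbuphine HCl ER treatment". The Statistical Methodology part of the synopsis lists n, mean, SD, median, minimum and maximum for vital signs and laboratory data, then adds: "The extent and duration of use of rescue medications will be similarly summarized using descriptive statistics". Nothing in the text available divides the count by time on drug or sets a common period.

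Time on drug is set elsewhere:

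- Section 9.6.2, entry at Visit 1a: "Patients who enter the Treatment Period on Visit 1a will be in the Treatment Period for up to 50 weeks".
- Section 9.6.2, later entry: "Patients who enter the Treatment Period from the Observation Period will be in the Treatment Period for up to 46 Treatment Weeks".
- Synopsis, failure to improve: "Beginning on TV 3 and at every subsequent Treatment Visit, patients with a Worst itch NRS equal to or greater than" the baseline score stop study drug. Section 9.6.2.2.1 places TV3 in Treatment Week 5.
- Section 9.7.6.1: "If a medication is prescribed for chronic anti-pruritic use of greater than 2 weeks, the subject should be discontinued".
- Section 9.6.2.1.1: patients who cannot tolerate the lowest twice-daily dose can be stopped at the Week 2 telephone contact.

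**The concern.** A count of days is comparable between patients only if they are observed for similar lengths of time, or if differences in observation time are unrelated to what is being counted. Neither condition is secured here. A non-improver can leave at Week 5 while an improver continues to Week 50. The rule on chronic anti-itch prescribing goes further, because one form of rescue use can itself close the window in which rescue use is counted.

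A low mean count could therefore mean that patients needed little rescue, or that many did not stay on drug long enough to accumulate days. The summary as worded cannot separate the two. A reader would naturally take a low mean as favourable, and it can become lower because more patients stopped early.

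**Working it through.** The plan states no rescue-day figure, so there is none to reproduce. The check compares counting time between patients and then carries assumed rates of use through it.

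**Inputs from the protocol**

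- Completer from Visit 1a: 50 weeks × 7 = 350 days (section 9.6.2).
- Visit 1b entrant: at most 46 × 7 = 322 days (section 9.6.2). With entry at Week 12 and the 50-week ceiling on combined time (section 9.6.3), 38 × 7 = 266 days.
- Failure to improve at TV3: four completed weeks = 28 days, or 25 to 31 with the ±3-day window (section 9.6).

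**Step 1. Ratio of counting time**

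- 350/28 = 12.5.
- With the window: 350/31 = 11.3 and 350/25 = 14.0.
- If 14 washout days are counted for both: 364/42 = 8.7.
- Visit 1b entrants against Visit 1a completers: 350/322 = 1.09 and 350/266 = 1.32. Late entry matters little; early stopping drives the difference.

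**Step 2. Counts at equal use**

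Expected count = share of days with rescue × days on drug. The shares are assumptions, because the documents give none.

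| Share of days | TV3 failure (28 days) | Completer (350 days) |
|---|---|---|
| 10% | 2.8 | 35 |
| 25% | 7 | 87.5 |
| 50% | 14 | 175 |

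A TV3 failure cannot score above about 28 days. A completer reaches 28 by using rescue on 28/350 = 8% of days.

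**Step 3. Counts at unequal use (assumed shares)**

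| TV3 failure / completer | Raw counts | Days per 28 on drug |
|---|---|---|
| 50% / 10% | 14 / 35 | 14.0 / 2.8 |
| 50% / 5% | 14 / 17.5 | 14.0 / 1.4 |
| 25% / 10% | 7 / 35 | 7.0 / 2.8 |
| 10% / 25% | 2.8 / 87.5 | 2.8 / 7.0 |
| 100% / 5% | 28 / 17.5 | 28.0 / 1.4 |

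In the first three rows the raw count reverses the order of the rates. In the fourth the order is right but the gap is inflated (87.5/2.8 = 31-fold against a true 2.5-fold). In the fifth the order is right, because the failure's rate is more than 12.5 times the completer's.

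**Step 4. Cohort mean**

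Let half the cohort stop at TV3 instead of none.

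- 50% / 10%: the mean count falls from 35.0 to 0.5 × 14 + 0.5 × 35 = 24.5. The mean per-patient share of days rises from 10% to 0.5 × 50% + 0.5 × 10% = 30%.
- 10% / 10%: the mean count falls from 35.0 to 0.5 × 2.8 + 0.5 × 35 = 18.9, although the rate of use is unchanged.
- 100% / 5%: the mean count rises from 17.5 to 0.5 × 28 + 0.5 × 17.5 = 22.75.

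The mean therefore falls with more TV3 stops unless failures use rescue at more than 12.5 times the completers' rate.

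**The case against.** The strongest reply is that scaling, interval tables and censoring belong in the SAP. Neither the SAP nor the statistical section of version 2.0 was available for this review, so an adjustment may exist there. That limit stands. It does not remove the point, because the protocol names the measure itself as a count of days over each patient's treatment, and an analysis that follows that wording inherits the problem.

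A second reply is that the count does what section 9.7.6.1 asks: "A secondary objective of the study is to quantitate the number of days of rescue medication use for itching". This is right. A reader might infer that the endpoint fails its stated objective, but the objective is the number of days, not need for rescue. The difficulty lies in comparing and averaging that number.

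A third reply concerns direction. A reader might infer that the mean is shown to be biased downward by treatment failures. The documents hold no rescue-use data that would show this. The failure rule rests on a Worst Itch score and not on rescue use, and effective rescue could lower that score and keep a heavy user on drug. Heavier use among early leavers is plausible, and the chronic-prescription rule points that way, but how many patients it would affect is unknown.

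Finally, the study has one arm and plans no tests. The same endpoint list reports failure to improve by time on study, discontinuation, and time to first rescue use. These show that truncation occurs, but they do not rescale the count.

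**Conclusion.** The point holds as a weakness in how a descriptive secondary endpoint is specified. The day count is not comparable across patients whose time on drug differs by a factor of 12.5 (11.3 to 14.0) between a TV3 failure and a Visit 1a completer, and by more if intolerance stops treatment earlier. That time is tied to outcome, and in one rule to anti-itch prescribing.

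The exposure ratio follows from the visit schedule alone. Every statement about the resulting error in the mean rests on assumed rates of use: across the cases shown, the mean count can fall while the rate rises, fall while the rate is constant, or rise with the rate. Time to first use does not share the flaw if patients who never use rescue are censored at end of treatment, but it does not measure how much was used. No hypothesis test, and nothing in the primary safety endpoint, is affected.

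**What to change.** Keep the raw count as a supporting figure or listing, and change the summarised measure:

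1. Report rescue days per 28 days on treatment, or the percentage of on-treatment days with rescue use. State whether this is the mean of per-patient rates or total rescue days over total days on drug. In the 50% / 10% case with half stopping at TV3 these are 30% and 24.5/189 = 13.0%.
2. Add the share of patients using rescue in each 4-week treatment interval among those still on drug, with the number at risk.
3. Censor time to first use at end of treatment.
4. State that washout days are excluded or reported separately. Section 9.6.5 collects the Rescue Medication Log at the washout visit, so it may include days off drug.
5. Confirm that the log reaches Visit 1b entrants. The log and Dosing Diary are dispensed in the Visit 1a list (section 9.6.1), but neither appears in the Visit 1b list (section 9.6.4).

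The first four items change wording and table shells only, provided the log records dates of use. The fifth is a check on data collection. No visit or stopping rule needs to change for this.
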